6.11.1. Criteria for Discontinuation of Study Treatment

Study medication may be discontinued in the following instances:

- Discharge from the hospital/institution
- Intercurrent illness that would, in the judgment of the investigator, affect assessments of clinical status to a significant degree. Following resolution of intercurrent illness, the subject may resume study dosing at the discretion of the investigator.
- Unacceptable toxicity, or toxicity that, in the judgment of the investigator, compromises the ability to continue study-specific procedures or is considered to not be in the subject's best interest
- Subject request to discontinue for any reason
- Subject noncompliance
- Pregnancy during the study; refer to [Appendix 3](#)
- Discontinuation of the study at the request of Gilead, a regulatory agency or an IRB or IEC

6.12. End of Study

The end of the study will be the last participant's last observation (or visit).

6.13. Post Study Care

The long-term care of the participant will remain the responsibility of their primary treating physician. Remdesivir is being supplied with curative intent. There is no provision for post-study availability.

6.14. Sample Disposition and Storage (Non-PK Samples)

Samples will be processed and retained according to local practice and the regulations pertaining to each institution. At participating sites, nasopharyngeal swab SARS-CoV-2 samples will be collected and sent to Gilead or its research partner for additional virologic testing. **CCI**

[REDACTED]

CCI [REDACTED]

[REDACTED]

7. ADVERSE EVENTS AND TOXICITY MANAGEMENT

7.1. Definitions of Adverse Events and Serious Adverse Events

7.1.1. Adverse Events

An AE is any untoward medical occurrence in a clinical study subject administered an investigational product, which does not necessarily have a causal relationship with the treatment. An AE can therefore be any unfavorable and/or unintended sign, symptom, or disease temporally associated with the use of an investigational product, whether or not considered related to the investigational product. AEs may also include pretreatment or posttreatment complications that occur as a result of protocol specified procedures or special situations (Section 7.6).

An AE does not include the following:

- Medical or surgical procedures such as surgery, endoscopy, tooth extraction, and transfusion. The condition that led to the procedure may be an AE and must be reported.
- Preexisting diseases, conditions, or laboratory abnormalities present or detected before the screening visit that do not worsen
- Situations where an untoward medical occurrence has not occurred (eg, hospitalization for elective surgery, social and/or convenience admissions)
- Overdose without clinical sequelae (Section 7.6.1)
- Any medical condition or clinically significant laboratory abnormality with an onset date before the consent form is signed and not related to a protocol-associated procedure is not an AE. It is considered to be preexisting and should be documented as medical history.
- Preexisting events or conditions that increase in severity or change in nature after the consent form is signed or as a consequence of participation in the clinical study will be considered AEs

7.1.2. Serious Adverse Events

A SAE is defined as an event that, at any dose, results in the following:

- Death
- Life-threatening (Note: The term “life-threatening” in the definition of “serious” refers to an event in which the subject was at risk of death at the time of the event; it does not refer to an event that hypothetically might have caused death if it were more severe)
- In-patient hospitalization or prolongation of existing hospitalization

- Persistent or significant disability/incapacity
- A congenital anomaly/birth defect
- A medically important event or reaction: such events may not be immediately life-threatening or result in death or hospitalization but may jeopardize the subject or may require intervention to prevent one of the other outcomes constituting SAEs. Medical and scientific judgment must be exercised to determine whether such an event is a reportable under expedited reporting rules. Examples of medically important events include intensive treatment in an emergency room or at home for allergic bronchospasm; blood dyscrasias or convulsions that do not result in hospitalization; and development of drug dependency or drug abuse.

7.2. Assessment of Adverse Events and Serious Adverse Events

The investigator or qualified subinvestigator is responsible for assessing AEs and SAEs for causality and severity, and for final review and confirmation of accuracy of event information and assessments.

7.2.1. Assessment of Causality for Study Drugs and Procedures

The investigator or qualified subinvestigator is responsible for assessing the relationship to study drug using clinical judgment and the following considerations:

- **No:** Evidence exists that the AE has an etiology other than the study drug. For SAEs, an alternative causality must be provided (eg, preexisting condition, underlying disease, intercurrent illness, or concomitant medication).
- **Yes:** There is reasonable possibility that the AE may have been caused by the study drug.

It should be emphasized that ineffective treatment should not be considered as causally related in the context of AE reporting.

The relationship to study procedures (eg, invasive procedures such as venipuncture or biopsy) should be assessed using the following considerations:

- **No:** Evidence exists that the AE has an etiology other than the study procedure.
- **Yes:** The AE occurred as a result of protocol procedures (eg, venipuncture).

7.2.2. Assessment of Severity

The severity of AEs will be graded using the Division of AIDS (DAIDS) Table for Grading the Severity of Adult and Pediatric Adverse Events, Version 2.1 dated July 2017. For each episode, the highest grade attained should be reported as defined in the grading scale. The DAIDS scale is available at the following location:

<https://rsc.niaid.nih.gov/sites/default/files/daidsgradingcorrectedv21.pdf>

7.3. Investigator Requirements and Instructions for Reporting Adverse Events and Serious Adverse Events

7.3.1. Requirements for Collection Prior to Study Drug Initiation

After informed consent, but prior to initiation of study medication, the following types of events must be reported on the applicable eCRFs: all SAEs and AEs related to protocol-mandated procedures.

7.3.2. Adverse Events

Following initiation of study medication, collect all AEs, regardless of cause or relationship, throughout the duration of the study, including the protocol-required post treatment follow-up period must be reported on the eCRFs as instructed.

All AEs and clinically significant laboratory abnormalities will be followed until resolution or stability of the abnormality has been demonstrated if possible. Gilead may request that certain AEs be followed beyond the protocol-defined follow-up period.

7.3.3. Serious Adverse Events

All SAEs, regardless of cause or relationship, that occurs after the subject first consents to participate in the study (ie, signing the informed consent) and throughout the duration of the study, including the protocol-required post treatment follow-up period, must be reported on the applicable eCRFs and Pharmacovigilance and Epidemiology (PVE) as instructed below in this section. This also includes any SAEs resulting from protocol-associated procedures performed after informed consent is signed.

Any SAEs and deaths that occur after the post-treatment follow-up visit but within 7-days of the last dose of study drug, regardless of causality, should also be reported.

Investigators are not obligated to actively seek SAEs after the protocol-defined follow-up period; however, if the investigator learns of any SAEs that occur after the protocol-defined follow-up period has concluded and the event is deemed relevant to the use of study drug, the investigator should promptly document and report the event to Gilead PVE.

- All AEs and SAEs will be recorded in the eCRF database within the timelines outlined in the eCRF completion guidelines.

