6.5. Day 28 Follow up Assessment (\pm 5 Days)

The following evaluations are to be completed if this visit is conducted in person. For participants who have been discharged from hospital, the final evaluation can be made by phone. Only AE and concomitant medication and ordinal scale (if discharged on or after Day 14) review are to be completed if visit is conducted by phone.

- Physical examination and vital signs (heart rate, temperature, blood pressure)
- Documentation of respiratory status:

Respiratory rate

— Oxygen supplementation: room air, low flow O₂ (L/min and %), high flow O₂ (L/min and %), CPAP/BIPAP (FiO₂ or %), mechanical ventilation (FiO₂ or %), ECMO

Oxygenation: SpO₂ or PaO₂

Radiographic findings (if available)

- Review AEs and document concomitant medications
- Review the Ordinal Scale (Section 6.9). If subject was not discharged by Day 14, any change in category and the date of any change in category from Day 14 to discharge (or Day 28) should be recorded

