8.1.4. Other Endpoints of Interest

Other endpoints of interest are:

- The proportion of participants with negative SARS-CoV-2 PCR
- Time to clinical improvement (days): clinical improvement is defined as a ≥ 2 -point improvement in clinical status (7-point ordinal scale) from Day 1
- Time to ≥ 1 -point improvement (days) from baseline clinical status
- Time to recovery: defined as an improvement in clinical status from a baseline score of 2 through 5 to a score of 6 or 7, or an improvement from a baseline score of 6 to a score of 7
- Time to modified recovery: defined as an improvement in clinical status from a baseline score of 2 through 4 to a score of 5, 6, or 7, or an improvement from a baseline score of 5 to a score of 6 or 7, or an improvement from a baseline score of 6 to a score of 7

- Time to room air: defined as an improvement in clinical status from a baseline score of 2 through 4 to a score of 5, 6, or 7
- Duration of oxygen therapy (days)
- Shift in oxygen support status from baseline
- Duration of hospitalization (days)
- All-cause mortality at Day 28

- The proportion of participants in the Extension Treatment Group with treatment emergent adverse events

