8.6.2. Adverse Events

Clinical and laboratory AEs will be coded using the Medical Dictionary for Regulatory Activities (MedDRA). System Organ Class (SOC), High-Level Group Term (HLGT), High-Level Term (HLT), Preferred Term (PT), and Lower-Level Term (LLT) will be attached to the clinical database.

Events will be summarized on the basis of the date of onset for the event. A treatment-emergent AE will be defined as any AE that begins on or after the randomization date up to the date of last dose of study drug plus 30 days, or up to Day 28, whichever is the later date.

Summaries (number and percentage of participants) of treatment-emergent adverse events (TEAEs) (by SOC, and PT) will be provided by treatment group.

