Appendix 2. Study Procedures Table

	Screening	Baseline / Day 1 ^b	Day 2	Day 3	Day 4	Day 5	Days 6 and 7	Day 8	Day 9	Day 10	Days 11, 12 and 13	Day 14	Day 28 ^c Follow-up (± 5 days)
Written Informed Consent	X												
Medical History	X												
Physical Examination	X	X	X	X	X	X	X	X	X	X	X	X	X
Height	X												
Vital Signs ^d	X	X	X	X	X	X	X	X	X	X	X	X	X
Study Laboratory Testing	X	X		X		X		X		X		X	
Respiratory Status	X	X	X	X	X	X	X	X	X	X	X	X	X
Ordinal Scale		X	X	X	X	X	X	X	X	X	X	X	X
Pregnancy Test	X												
CCI													
Virologic Testing ^e		X		X		X		X		X		X	
RDV Dosing for Group 1		X	X	X	X	X							
RDV Dosing for Group 2		X	X	X	X	X	X	X	X	X			
Adverse Events	X	X	X	X	X	X	X	X	X	X	X	X	X
Concomitant Medications	X	X	X	X	X	X	X	X	X	X	X	X	X

- a Includes heart rate, respiratory rate, temperature, blood pressure, SpO₂, and body weight. Body weight collected on Screening and Day 1 and otherwise if available.
- b Assessments need not be repeated if performed within 24 hours of screening procedures; data collection other than adverse events and concomitant medications should stop at Day 14 or discharge, whichever is earlier.
- c Day 28 evaluations completed if the visit is conducted in person. Only adverse event and concomitant medications review completed if visit conducted by phone.
- d [REDACTED]
- e Virologic (SARS CoV 2) testing for subjects/sites participating in this portion of the study on Days 1, 3, 5, 8, 10, and 14.

Appendix 3. Pregnancy Precautions, Definition for Female of Childbearing Potential, and Contraceptive Requirements

1) Definitions

a. Definition of Childbearing Potential

For the purposes of this study, a female born subject is considered of childbearing potential following the initiation of puberty (Tanner stage 2) until becoming post-menopausal, unless permanently sterile or with medically documented ovarian failure. No documentation of Tanner stage will be required for people unless deemed prepubescent.

Women are considered to be in a postmenopausal state when they are ≥ 54 years of age with cessation of previously occurring menses for ≥ 12 months without an alternative cause. In addition, women of any age with amenorrhea of ≥ 12 months may also be considered postmenopausal if their follicle stimulating hormone (FSH) level is in the postmenopausal range and they are not using hormonal contraception or hormonal replacement therapy.

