7.2.6. Summaries of Adverse Events and Deaths

The number and percentage of participants who experienced at least 1 TEAE will be provided and summarized by system organ class, HLT, and PT. For other AEs described below, summaries will be provided by system organ class and PT using the Expanded RDV-Treated Analysis Set:

- Grade 3 or higher treatment-emergent AEs
- All treatment-emergent study drug-related AEs
- Grade 3 or higher treatment-emergent study drug-related AEs
- All treatment-emergent SAEs
- All treatment-emergent study drug-related SAEs
- All treatment-emergent AEs that caused premature discontinuation from study drug
- Treatment-emergent deaths

A brief, high-level summary of AEs described above will be provided by the number and percentage of participants who experienced the above AEs. Treatment-emergent deaths observed in the study will also be included in this summary.

Treatment-emergent death refers to deaths that occurred between the first dose date and the last dose date plus 30 days (inclusive).

Multiple events will be counted only once per participant in each summary. Adverse events will be summarized and listed first in alphabetic order of system organ class and HLT within each system organ class (if applicable), and then by PT in descending order of total frequency within each system organ class. For summaries by severity grade, the most severe grade will be used for those AEs that occurred more than once in an individual participant during the study.

In addition to the above summary tables, all treatment-emergent AEs, treatment-emergent AEs with Grade 3 or higher, treatment-emergent study drug-related AEs, treatment-emergent study drug-related AEs with Grade 3 or higher, and treatment-emergent SAEs will be summarized by PT only, in descending order of total frequency. Preferred terms with the same total frequency will be sorted in alphabetical order. Treatment-emergent AEs and study-drug related treatment-emergent AEs will also be summarized by highest grade.

Data listings will be provided for the following:

- All AEs
- Study-Drug-Related AEs
- AEs with severity of Grade 3 or higher
- SAEs
- Study-Drug-Related SAEs
- Deaths
- AEs leading to premature discontinuation of study drug

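### The 7-day catch-up rule for late SAEs and deaths covers no days on any scheduled regimen, the treatment-emergent window outlasts follow-up after a full course, and Day 28 vital status is not assured when the last contact is early

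*Protocol*

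**What the plan says.** **Visit.** Protocol 6.5 ("Day 28 Follow up Assessment") and Appendix 2 place the only follow-up contact at Day 28 with a 5-day allowance either side. Protocol 6.5 adds: "For participants who have been discharged from hospital, the final evaluation can be made by phone". Protocol 6.10 requires nothing after Day 28.

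**Reporting.** Protocol 7.3.3 requires all SAEs, whatever the cause, to be reported from consent through the post-treatment follow-up period, but does not give the day on which that period ends. It then adds "Any SAEs and deaths that occur after the post-treatment follow-up visit but within 7-days of the last dose of study drug". Beyond follow-up, investigators need not look for SAEs. They report those they learn of and consider relevant to study drug.

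**Dosing.** Protocol 5.3 schedules the last dose on Day 5 (Treatment Group 1) or Day 10 (Treatment Group 2 and the Extension Treatment Group).

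**Analysis windows.** Protocol 8.6.2 counts an AE as treatment-emergent "up to the date of last dose of study drug plus 30 days, or up to Day 28, whichever is the later date". Protocol 8.6 summarises safety data only through the Day 28 follow-up visit. For Part B, SAP 7, 7.2.5.1 and 7.2.6 use 30 days after the last dose for safety data, TEAEs and treatment-emergent deaths.

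**Mortality.** Protocol 8.1.4 lists "All-cause mortality at Day 28" among the other endpoints of interest.

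**The concern.** A clause that picks up SAEs and deaths after the last visit is there to close the gap between the end of visits and the end of the safety window. This one looks back to the last dose by a period that has already run out before the visit can occur, so it cannot do that on the planned schedule. The window that the analysis uses is meanwhile more than four times as long (30 days against 7).

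Two results are exposed. The first is the proportion with TEAEs, which is the trial's only secondary endpoint. In Part A it is compared between each RDV group and SOC by Fisher's exact test (Protocol 8.5.2). The stated window promises more observation time than is collected, and it differs by arm. The second is Day 28 mortality. A discharged participant may be telephoned on Day 23 and not contacted again.

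**Working it through.** The plan states no figure for follow-up coverage, so there is none to reproduce. The check is day counting.

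**Inputs**
- Visit day V: 28 − 5 = Day 23 at the earliest, 28 + 5 = Day 33 at the latest (Protocol 6.5, Appendix 2).
- Last dose L: Day 5 or Day 10 for a full course (Protocol 5.3). A single dose (L = 1) is shown as the shortest case, because RDV stops at discharge.
- First dose on Day 1, as the protocol synopsis and SAP 1.2 expect.
- The follow-up visit named in Protocol 7.3.3 is the Day 28 visit, the only one in the schedule with that role.

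**Step 1: the 7-day clause.** It needs an event after V and no later than L + 7.
- 10-day course: 10 + 7 = Day 17, and 23 − 17 = 6 days before the earliest visit.
- 5-day course: 5 + 7 = Day 12, and 23 − 12 = 11 days before it.
- Days covered: 0 in both cases. For the clause to apply, L would have to be at least 23 − 7 = Day 16 (event later on the visit day) or 24 − 7 = Day 17 (event the next day).

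**Step 2: the treatment-emergent window.** It ends at E = max(L + 30, 28). The days after the visit are max(0, E − V).

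| Group | E | V = 23 | V = 28 | V = 33 |
|---|---|---|---|---|
| 10-day course | 40 | 17 | 12 | 7 |
| 5-day course | 35 | 12 | 7 | 2 |
| Single dose | 31 | 8 | 3 | 0 |
| SOC (no dose) | 28 | 5 | 0 | 0 |

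No permitted visit reaches the end of the window when L + 30 > 33, that is, when the last dose is on Day 4 or later. Every completed course is in that position.

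**Step 3: Day 28 vital status.** The days unobserved are max(0, 28 − V): 5 for a visit on Day 23, falling to 1 for Day 27, and 0 from Day 28 on.

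**Step 4: what the Part B analyses do with an early contact.** SAP 6.2 sets a participant discharged alive to category 7 (not hospitalized) through Day 28 unless a death is recorded. SAP 6.2.1 estimates mortality by Kaplan-Meier and censors survivors at the last study day. The ordinal summary therefore fills in the unobserved days, and the mortality estimate does not.

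**The case against.** A reader might infer several stronger statements. The documents do not support them.

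- *The clause can never apply.* Protocol 6.11.1 lets dosing resume after an intercurrent illness and states no last calendar day. A last dose on Day 16 or later is not strictly excluded, so the claim holds only for the scheduled regimens.
- *Late serious events have no collection rule.* Death is an SAE (Protocol 7.1.2). Protocol 7.3.3 requires all-cause SAE reporting throughout follow-up, which can be read as running to Day 28, and passive reporting of relevant SAEs after that. What the tail lacks is active follow-up and an all-cause duty to report.
- *Day 28 mortality is not ascertained.* The gap is at most 5 days and arises only for contacts on Days 23 to 27. For participants not discharged by Day 14, Protocol 6.5 has category changes, death among them, recorded to discharge or Day 28. The exposure is mainly among discharged participants contacted early.
- *A Part A participant last seen on Day 23 is counted as alive at Day 28.* Protocol 8.5.2 names chi-square or Fisher tests for proportions but does not say how an early last contact is classified. The Part A Primary Analysis SAP, cited in SAP 2.1.2, is not among the documents supplied.
- *RDV harm is under-counted relative to SOC.* All Part A arms share one visit schedule. The RDV windows are less completely covered, but an event after Day 28 that a site happens to learn of can count only in an RDV arm. The direction of any bias cannot be settled.

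It can also be argued that the 30-day term only labels events and does not promise follow-up to Day 40. That is a fair reading of Protocol 8.6.2. Even so, Protocol 7.3.3, 8.6 and 8.6.2 give three different end points, and SAP 7 summarises safety data to 30 days after the last dose.

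**Conclusion.** The point holds in this form. On every scheduled regimen the 7-day clause covers no days. After a full RDV course the treatment-emergent window outlasts the visit by 7 to 17 days (10-day) or 2 to 12 days (5-day), with passive and relevance-filtered SAE reporting only. Vital status at Day 28 is not assured for discharged participants whose last contact is on Days 23 to 27, with at most 5 days unobserved.

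This rests on a first dose on Day 1, dosing as scheduled, and the Day 28 visit being the one meant in Protocol 7.3.3. The documents do not say how many contacts precede Day 28, so neither the number of participants affected nor the number of events missed can be computed. The primary endpoint, at Day 11, is untouched. The weight comes from the secondary TEAE comparison and the ease of the correction. Day 28 mortality is only an other endpoint of interest.

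**What to change.** 1. Hold the existing contact on Day 28 to Day 33, or keep the present allowance and otherwise confirm and record vital status as of Day 28. Either closes the mortality gap.
2. Bring Protocol 7.3.3, 8.6 and 8.6.2 and SAP 7, 7.2.5.1 and 7.2.6 to one window. One option is to end the treatment-emergent window at the follow-up actually performed, in all arms. The other is to replace the 7-day clause with all-cause SAE and death reporting to 30 days after the last dose, and to state that events after the visit are captured passively.

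Step 1 alone does not settle step 2. With contact on Days 28 to 33, 7 to 12 days of the window still lie beyond it after a 10-day course, and 2 to 7 days after a 5-day course. Of the two options, only the first removes the uncovered tail. The second makes reporting in it all-cause and discloses that it is passive.

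Cost: no added visit. Some phone contacts move up to 5 days later, and there is either slightly longer reporting or a shorter stated safety window.
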